3.2 Exclusion Criteria

Participants who exhibit any of the following conditions at screening will not eligible for admission into the study:

3.2.1 Patients currently receiving anticancer therapies or who have received anticancer therapies within 28 days of the start of study drug (including chemotherapy, radiation therapy, antibody based therapy, etc.), or 56 days for radioimmunotherapy. Steroids for symptom palliation are allowed, but must be either discontinued or on stable doses of ≤ 10 mg daily of prednisone (or the equivalent) at the time of initiation of protocol therapy.

- 3.2.2 Patients may not be receiving any other investigational agents, or have received investigational agents within 4 weeks (or 3 half-lives, whichever is longer) of beginning treatment.
- 3.2.3 History of severe allergic or anaphylactic reactions to monoclonal antibody therapy unless in consultation with an allergy specialist they are deemed eligible for retreatment with desensitization.
- 3.2.4 Patients who have previously received therapy with any drug that works by a similar mechanism of action as any drug being tested in a given cohort will be excluded from that cohort but will be allowed to enroll in other open cohorts.
- 3.2.5 Patients who have undergone prior allogeneic stem cell transplantation
- 3.2.6 Patients with a history of or active autoimmune disease (except controlled asthma, Hashimoto thyroiditis, atopic dermatitis, and/or vitiligo), or requiring systemic corticosteroids at a dose of 10mg prednisone equivalent daily. Patients with a history of autoimmune disease who never required corticosteroids and with no evidence of disease activity, and in whom the risk of reactivation is felt not to be serious, may be enrolled after discussion with the overall study chair. Exceptions to this are patients with a history of inflammatory bowel disease (ulcerative colitis and Crohn's disease). These patients are excluded regardless of whether their disease is active or inactive.
- 3.2.7 Patients with active pneumonitis or colitis, or patients with chronic liver disease and/or cirrhosis
- 3.2.8 Patients, who have had a major surgery or significant traumatic injury within 4 weeks of start of study drug, patients who have not recovered from the side effects of any major surgery (defined as requiring general anesthesia) or patients that may require major surgery during the course of the study.

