- 3.2.9 Patients with known leptomeningeal or brain metastases. Imaging or spinal fluid analysis to exclude CNS involvement is not required, unless there is clinical suspicion by the treating investigator.
- 3.2.10 Patients with known HIV infection or hepatitis B or C infection. Testing for HIV is optional. Testing for hepatitis B and C is mandatory. Patients with hepatitis B core Ab positivity but negative surface antigen and negative viral load may be enrolled if they can be treated with a prophylactic agent (eg, entecavir); patients with hepatitis C seropositivity who have undergone successful treatment with negative viral load can also be enrolled.
- 3.2.11 Patients with a systemic fungal, bacterial, viral, or other infection not controlled (defined as exhibiting ongoing signs/symptoms related to the infection and without improvement, despite appropriate antibiotics or other treatment).
- 3.2.12 Prior history of another malignancy (except for non-melanoma skin cancer or *in situ* cervical or breast cancer) unless disease free for at least three years. Patients with prostate cancer are allowed if PSA is less than 1.
- 3.2.13 Patients should not have received immunization with attenuated live vaccine within one week of study entry or during study period.

- 3.2.14 Female patients who are pregnant or breast feeding, or adults of reproductive potential who are not using effective birth control methods. Women of child bearing potential (WOCBP) or male study participants of reproductive potential must agree to use double barrier birth control method of contraception during the course of the study treatment period and for 3 months after completing study treatment. WOCBP are defined as sexually mature women who have not undergone a hysterectomy or who are not postmenopausal (no menses) for at least 12 consecutive months. WOCBP must have a negative urine or serum pregnancy test within 14 days prior to administration of treatment.
- 3.2.15 History of noncompliance to medical regimens.
- 3.2.16 Patients who have any severe and/or uncontrolled medical conditions or other conditions that could affect their participation in the study such as:
 - New York Heart Association Class III or IV cardiac disease, including preexisting clinically significant arrhythmia, congestive heart failure, or cardiomyopathy

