5.2 Treatment Regimen

It is expected that treatment will be administered on an outpatient basis. A cycle will be 28 days and there will be a planned 6 cycles of therapy. Therapy will consist of the following, with each cohort consisting of 15 patients each:

5.2.1 Cycle 1

Cohort Ala:

- (i) Rituximab (or rituximab biosimilar) 375 mg/m²/dose intravenously per institutional standards for four weekly treatments for cycle 1 only, starting on day -6.
- (ii) Utomilumab 100mg intravenously over 1 hour on day 2.
- (iii) Avelumab 3mg/kg (dose level 1) or 10mg/kg (dose level 2) intravenously over 1 hour on day 16.

Cohort Alb and B1:

- (i) Rituximab (or rituximab biosimilar) 375 mg/m²/dose intravenously per institutional standards for four weekly treatments for cycle 1 only, starting on day -6.
- (ii) Utomilumab 100mg intravenously over 1 hour on day 2.
- (iii) Avelumab at the recommended phase 2 dose intravenously over 1 hour on day 16.

Cohort A2a, Dose Level 0:

(i) PF-04518600 0.3mg/kg intravenously over 1 hour on day 1 and day 15.

Cohort A2a, Dose Level 1:

- (i) Rituximab (or rituximab biosimilar) 375 mg/m²/dose intravenously per institutional standards for four weekly treatments for cycle 1 only, starting on day -6.
- (ii) PF-04518600 0.3mg/kg intravenously over 1 hour on day 2 and day 16.

Cohort A2a, Dose Level 2:

- (i) Rituximab (or rituximab biosimilar) 375 mg/m²/dose intravenously per institutional standards for four weekly treatments for cycle 1 only, starting on day -6.
- (ii) Utomilumab 100mg intravenously over 1 hour on day 2.
- (iii) PF-04518600 0.3mg/kg intravenously over 1 hour on day 16.

Cohort A2b and B2:

- (i) Rituximab (or rituximab biosimilar) 375 mg/m²/dose intravenously per institutional standards for four weekly treatments for cycle 1 only, starting on day -6.
- (ii) Utomilumab 100mg intravenously over 1 hour on day 2.
- (iii) PF-04518600 0.3mg/kg intravenously over 1 hour on day 16.

Cohort A3a:

(i) Rituximab (or rituximab biosimilar) 375 mg/m²/dose intravenously per institutional standards for four weekly treatments for cycle 1 only, starting on day -6.

- (ii) PF-04518600 0.3mg/kg intravenously over 1 hour on day 2 and day 15. PF-04518600 will be given first and must have completed administration at least 30 minutes (but a maximum of 28 hours) prior to rituximab (day 15)
- (iii) Avelumab 3mg/kg (dose level 1) or 10mg/kg IV (dose level 2) over 1 hour on day 16.

Cohort A3b:

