- (i) Rituximab (or rituximab biosimilar) 375 mg/m²/dose intravenously per institutional standards for four weekly treatments for cycle 1 only, starting on day -6.
- (ii) PF-04518600 0.3mg/kg intravenously over 1 hour on day 2 and day 15. PF-04518600 will be given first and must have completed administration at least 30 minutes (but a maximum of 28 hours) prior to rituximab (day 15)
- (iii) Avelumab at the recommended phase 2 dose intravenously over 1 hour on day 16.

5.2.2 Cycle 2-6

Cohort Ala:

- (i) Utomilumab 100mg intravenously over 1 hour once every 4 weeks x 5 (up to 5 additional doses) on day 1 of each cycle. Utomilumab must have completed administration at least 30 minutes (but a maximum of 28 hours) prior to avelumab.
- (ii) Avelumab 3mg/kg (dose level 1) or 10mg/kg (dose level 2) intravenously over 1 hour once every 2 weeks x 10 (up to 10 additional doses), on day 1 and day 15 of each cycle. On days when avelumab will be given in combination with utomilumab it must be given at least 30 minutes (maximum 24+/-4 hours) following the completion of utomilumab.

Cohort A1b and B1:

- (i) Utomilumab 100mg intravenously over 1 hour once every 4 weeks x 5 (up to 5 additional doses) on day 1 of each cycle. Utomilumab must have completed administration at least 30 minutes (but a maximum of 28 hours) prior to avelumab.
- (ii) Avelumab at the recommended phase 2 dose intravenously over 1 hour once every 2 weeks x 10 (up to 10 additional doses), on day 1 and day 15 of each cycle. On days when avelumab will be given in combination with utomilumab it must be given at least 30 minutes (maximum 24+/-4 hours) following the completion of utomilumab.

Cohort A2a, Dose level 0:

- (i) PF-04518600 0.3mg/kg intravenously over 1 hour on day 1 and day 15.
 - **If there is no response on midtreatment scans following cycle 3, patients may get Rituximab (or rituximab biosimilar) 375mg/m2 intravenously on day 1, 8, 15, and 22 of cycle 4, with PF-04518600 0.3mg/kg intravenously over 1 hour on day 1 and day 15 of this cycle. On days when rituximab will be given in combination with PF-04518600 it must be given at least 30 minutes (maximum 28 hours) following the completion of PF-04518600.

Cohort A2a, Dose level 1:

(i) PF-04518600 0.3mg/kg intravenously over 1 hour on day 1 and day 15.

Cohort A2a, Dose level 2:

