5.3 General Concomitant Medication and Supportive Care Guidelines

Medications or vaccinations specifically prohibited in the exclusion criteria are also not allowed during the active treatment period, except for administration of inactivated vaccines (for example, inactivated influenza vaccine). If there is a clinical indication for one of these or other medications or vaccinations specifically prohibited during the trial, permanent discontinuation from study therapy may be required. The Investigator should consult with the Principal investigator about individual cases. The final decision on any supportive therapy or vaccination rests with the Investigator and/or the patient's primary physician. However, the decision to continue the patient on study therapy or medication/vaccination schedule requires the mutual agreement of the Investigator, the Principal investigator, and the patient. Prior/concomitant treatment considered necessary for the patient's well-being may be given at discretion of the treating physician.

Concomitant medications and treatments, including herbal supplements, will be recorded from 28 days prior to the start of study treatment and up to 90 days after the last dose of study treatment (at Days 30, 60, and 90 post-treatment +3 days). Non-Drug Supportive Interventions should be recorded in the CRF including supportive care drugs (eg, antiemetic treatment and prophylaxis), and the drugs used to treat adverse events or chronic diseases, and non-drug supportive interventions (eg, transfusions).

Medications intended solely for supportive care (ie, antiemetics, analgesics, megestrol acetate for anorexia) are allowed.

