5.3.2 Antibiotics

Prophylactic antibiotics or anti-virals are not required on this trial.

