5.3.5 Other supportive treatments

Growth factors, blood product transfusions, and the use of bisphosphonates are permitted at the discretion of the treating physician.

Palliative and supportive care for disease related symptoms may be administered at the investigator's discretion and according to any available American Society of Clinical Oncology (ASCO) guidelines.

Patients should receive appropriate supportive care measures as deemed necessary by the treating Investigator including but not limited to the items outlined below:

- Diarrhea: All patients who experience diarrhea should be advised to drink liberal quantities of clear fluids. If sufficient oral fluid intake is not feasible, fluid and electrolytes should be substituted via IV infusion;
- Nausea/Vomiting: Nausea and vomiting should be treated aggressively, and consideration should be given in subsequent cycles to the administration of prophylactic antiemetic therapy according to standard institutional practice. Patients should be strongly encouraged to maintain liberal oral fluid intake.
- Anti-infectives: Patients with a documented infectious complication should receive oral or IV antibiotics or other anti-infective agents as considered appropriate by the treating Investigator for a given infectious condition, according to standard institutional practice. Prophylactic administration should be considered for the cases outlined in Table 2, Management of Immune Related Adverse Events;
- Anti-inflammatory or narcotic analgesics may be offered as needed.

Patients who need to be on anticoagulant therapy during treatment should be treated with low molecular weight heparin. If low molecular weight heparin cannot be administered, coumadin or other coumadin derivatives or other anticoagulants (including direct Xa inhibitors) may be allowed; however, appropriate monitoring of prothrombin time/international normalized ratio (PT/INR) should be performed.

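### Section 3.2.10 admits hepatitis B core-antibody-positive patients who can be given prophylaxis, but nothing in the available text directs that it be given, and 5.3.2 says without exception that anti-virals are not required

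*Combined protocol and SAP*

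**What the plan says.** Section 3.2.10 excludes known hepatitis B infection but makes an exception. Core-antibody-positive patients with negative surface antigen and negative viral load "may be enrolled if they can be treated with a prophylactic agent (eg, entecavir". The list in section 3.2 is applied at screening: "Participants who exhibit any of the following conditions at screening will not eligible for admission into the study".

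Section 5.3.2, in the treatment plan, consists of one sentence: "Prophylactic antibiotics or anti-virals are not required on this trial".

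Section 5.3 adds a general permission: "Prior/concomitant treatment considered necessary for the patient's well-being may be given at discretion of the treating physician". Section 5.3.5 mentions prophylaxis once, for immune-related events: "Prophylactic administration should be considered for the cases outlined in Table 2, Management of Immune Related Adverse Events".

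Most regimens in section 5.2 begin with rituximab: "four weekly treatments for cycle 1 only, starting on day -6". Cohort A2a dose level 0 starts with PF-04518600 alone. There, if mid-treatment scans show no response, "patients may get Rituximab (or rituximab biosimilar) 375mg/m2 intravenously on day 1, 8, 15, and 22 of cycle 4".

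**The concern.** An eligibility condition that a patient be treatable with an antiviral has little purpose unless the antiviral is then given. The treatment plan never says so, and its only sentence that names anti-virals points the other way. A site could admit a patient because entecavir is possible, follow 5.3.2, give nothing, and comply with both sections. Monitoring would then have no deviation to find.

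The protocol itself recognises the hazard. Section 7.1.1.4 lists hepatitis in carriers of the virus among the rare rituximab toxicities, and Table 4 stops all four drugs permanently for viral hepatitis B of any grade. At stake is a preventable harm in a subgroup that the protocol deliberately admits.

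**Working it through.** No arithmetic applies. The check is whether any provision in the available text turns the eligibility condition into a treatment instruction.

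**Is the agent ordered anywhere?**

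- 3.2.10: tests ability to be treated, at screening. Gives no instruction for the treatment period.
- 5.3: permits necessary treatment at the physician's discretion. Does not require it.
- 5.3.2: says anti-virals are not required. No exception is stated.
- 5.3.5 and Table 2: call for prophylactic antibiotics in the management of immune-related events. They say nothing about antivirals or hepatitis B.
- Table 4: acts once hepatitis B has occurred. Gives no preventive instruction.
- 8.2.4 (rituximab administration): covers premedication and infusion handling only.
- Study calendars and 10.1 to 10.4: no prophylaxis entry. Hepatitis B and C testing is marked at baseline only, with no repeat listed.

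None of these orders the agent. Table 2 is a useful contrast: where this protocol wants prophylaxis given, it says to add it.

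**What limits the risk without it?**

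- At entry: negative surface antigen and viral load (3.2.10), exclusion of chronic liver disease and cirrhosis (3.2.7), AST/ALT limits (3.1.9), laboratory eligibility to be met again on day -6 (10.2), and eligibility review before registration (4.4; Appendix C 3.7.1). These check who enters, not whether the agent is given.
- On study: a complete metabolic panel at each planned cycle 1 visit and on days 1 and 15 of cycles 2 to 6 (10.2), at end of treatment (10.3) and every 3 months in follow-up (10.4).
- Stopping rules: Table 2 withholds immunotherapy for grade 2 liver-test elevation and stops it permanently at grade 3 to 4. Table 4 stops all drugs for grade 3 or higher liver-test abnormality and, as a separate trigger, for hepatitis B of any grade.

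The panels and stopping rules detect and respond. They shorten the time to recognition but do not do what prophylaxis does.

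**When should prophylaxis start?** A start tied to the first rituximab dose works where rituximab is given on day -6, because that is also the first study dose. It fails in A2a dose level 0: a patient who responds, or does not take the cycle 4 option, has no rituximab dose and so no start time. A start tied to the first dose of any study treatment covers every cohort.

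**The case against.** The strongest reply is that the two sections do not conflict. Section 5.3.2 is a trial-wide default; it does not forbid the agent and does not address the 3.2.10 subgroup. The protocol already lets specific provisions override that default, since Table 2 calls for prophylactic antibiotics despite it. The wording of 3.2.10 also suits a screening list, because prophylaxis still lies ahead at that point. Harm would need an investigator to admit a patient because the agent can be given and then withhold it on the strength of a generic sentence, although 5.3 allows it.

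Much of this stands. The intent is reasonably clear and the gap is one of wording. What does not follow is that 3.2.10 overrides 5.3.2 during treatment: it contains no treatment instruction that could do so, whereas Table 2 does.

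A reader might infer more than the text supports:

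- *That the sponsor means to treat these patients unprotected, or that 5.3.2 prohibits prophylaxis.* Naming an agent in 3.2.10 and permitting necessary treatment in 5.3 both point the other way.
- *That reactivation would go unseen.* The scheduled panels and the separate hepatitis B stopping rule say otherwise, although no repeat hepatitis B test is listed.
- *That counts of rituximab-containing dose levels, or the length of the medication-recording window, measure the problem.* They do not, because the documents give neither the number of core-antibody-positive patients nor a prophylaxis duration.

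**Conclusion.** The point holds as a minor patient-safety consistency correction. The eligibility section presupposes prophylaxis, the treatment plan says without exception that it is not required, and no available text directs that it be given. A literal reading therefore allows omission without a deviation.

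It affects only patients admitted under the core-antibody provision of 3.2.10 whose site takes 5.3.2 at its word. The documents do not allow that number to be estimated, and none is claimed. No sample size, error rate or decision rule in section 13 changes.

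The conclusion rests on two assumptions: that the sponsor intends the agent to be given, which is an inference from 3.2.10, and that no instruction lies in parts of the protocol not available for this review.

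**What to change.** Two wording changes:

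1. In 3.2.10, replace *can be treated* with *will be treated*. This does not require the agent to be running at screening.
2. In 5.3.2, keep the general statement and add: *except that patients enrolled under the hepatitis B core-antibody provision of 3.2.10 must receive antiviral prophylaxis, started before the first dose of any study treatment (in all cohorts, including A2a dose level 0)*. The sponsor's clinicians should set the duration, since the documents give none.

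The cost is small. The amendment needs IRB approval at the participating institutions (Appendix C 3.2). In A2a dose level 0, some patients would take prophylaxis and never receive rituximab; that is the price of a start time that applies to everyone. The changes add no visits or tests. Section 5.3 already records concomitant medication from 28 days before study treatment, so whether the agent was started on time can be checked from existing data. Section 13 stays as it is.

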3.3 Inclusion of Women and Minorities

Women, minorities and underrepresented populations should be eligible for this trial at a similar rate to men and patients not from underrepresented populations. The inclusion and exclusion criteria should not be affected by gender or ethnicity, except for the exclusion of pregnant or lactating women.

4. REGISTRATION PROCEDURES

4.1 General Guidelines for DF/HCC Institutions

Institutions will register eligible participants in the Clinical Trials Management System (CTMS) OnCore. Registrations must occur prior to the initiation of any protocol-specific therapy or intervention. Any participant not registered to the protocol before protocol-specific therapy or intervention begins will be considered ineligible and registration will be denied.

An investigator will confirm eligibility criteria and a member of the study team will complete the protocol-specific eligibility checklist.

Following registration, participants may begin protocol-specific therapy and/or intervention. Issues that would cause treatment delays should be discussed with the Overall Principal Investigator (PI). If the subject does not receive protocol therapy following registration, the subject must be taken off-study in the CTMS (OnCore) with an appropriate date and reason entered.

4.2 Registration Process for DF/HCC Institutions

Applicable DF/HCC policy (REGIST-101) must be followed.

4.3 General Guidelines for Other Investigative Sites

Eligible participants will be entered on study centrally at the Dana-Farber Cancer Institute by the Project Manager. All sites should email the Project Manager at [contact] to verify dose level availabilities.

Following registration, participants should begin protocol therapy within 72 hours or as soon as possible. Issues that would cause treatment delays should be discussed with the Overall Principal Investigator. Issues that would cause treatment delays should be discussed with the Principal Investigator. If a participant does not receive protocol therapy following registration, the participant's protocol status must be changed. The Project Manager should be notified of participant status changes as soon as possible. Except in very unusual circumstances, each Participating Institution will order the study agent(s) directly from the supplier. A Participating Institution may order the agent(s) only after the initial IRB approval for the site has been forwarded by Coordinating Center to the supplier.

4.4 Registration Process for Other Investigative Sites

To register a participant, the following documents should be completed by the participating site and or e-mailed to [contact]:

- Copy of required laboratory tests required at screening (see study calendar)
- Signed informed consent document
- HIPAA authorization form (if separate from the informed consent document)

• Completed Eligibility Checklist

The participating site will then e-mail [contact] to verify eligibility. The Project Manager will follow DF/HCC policy (REGIST-101) and register the participant on the protocol. The Project Manager will e-mail the participant study number, and if applicable the dose treatment level, to the participating site. The Project Manager will also contact the participating site and verbally confirm registration

Treatment may not begin without confirmation from the Coordinating Center that the participant has been registered.

